5.3. Hypotheses

Applicable, null hypothesis: the risk of spontaneous abortion in exposed women is equal to the risk of spontaneous abortion in women from the non-exposed cohort.

Alternative hypothesis: the risk of spontaneous abortion in exposed women is higher than the risk of spontaneous abortion in women from the non-exposed cohort.

5.4. Sample size calculation

Using a two-sided log-rank test with type I error rate of 5% (Software: PASS 2005) and results from the feasibility analysis which has estimated the potential eligible subjects (see section 3.2), the study would have the following power to detect a relative risk (Hazard ratio, HR) of 2.0 of spontaneous abortion between the exposed and non-exposed subjects: 98% power if the first day of LMP is between 30 days before and 45 days after and 99% power if the first day of LMP is between 30 days before and 90 days after any dose of *Cervarix*. The HR detectable with 80% power would be 1.69 and 1.60, respectively.

Those calculations are based on the following assumptions:

- Rate of spontaneous abortion: approximately 11.5% of pregnancies (see section 3.2, feasibility analysis).
- Proportion of dropped out subjects before the first 23 weeks of gestation: 20%.

5.5. Statistical methods

Examples of statistical tables and figure templates are given in Appendix B.

5.5.1. Subject disposition

Subject disposition will be summarized by computing:

- Number of screened subjects.
- Number (%) of non-eligible subjects for each of the following reasons of non-eligibility:
 - No certainty of *Cervarix* vaccination
 - All *Cervarix* doses outside September 1th 2008 and June 30th 2011
 - No pregnancy identifiers
 - First day of LMP outside September 1th 2008 and June 30th 2011
 - Age at first day of LMP outside 15 – 25 years
 - Start in CPRD **GOLD** less than one year before first day of LMP
 - Subject not flagged as acceptable in CPRD **GOLD**
 - Neither in the exposed nor non-exposed cohort.
- Number of eligible subjects in each cohort.
- Number of included subjects in each cohort.

A detailed, comprehensive list of reasons for elimination from exposed and non-exposed cohort analyses will be established at the time of data cleaning.

(Amended 14 March 2013)

5.5.2. Demographic and baseline characteristics

Demographic and baseline characteristics of all included subjects (age at first day of gestation, age at vaccination, marital status, smoking, alcohol consumption, region (GP practice)) will be summarized per cohort and overall, using descriptive statistics.

Frequency tables will be generated for categorical variables.

Mean, standard error, median and range, will be provided for continuous variables.

Medical condition during pregnancy (diabetes, high blood pressure) will be summarized in a frequency table.

Availability of data in CPRD **GOLD** will be summarized by descriptive statistics: proportion of Baby and Mother links.

Proportion of subjects with first day of LMP before, during and after H1N1 pandemic in the UK (June 1st 2009 to February 28th 2010 according to Pebody [Pebody, 2010]).

The two cohorts will be compared for their demographic and baseline characteristics using Fisher's exact test or Student t-test.

(Amended 14 March 2013)

5.5.3. Pregnancy outcomes

5.5.3.1. Endpoints related to spontaneous abortion

Proportion of spontaneous abortion will be calculated for the exposed and the non-exposed cohorts as the number of pregnant women with spontaneous abortion divided by the total number of included pregnant women.

The risk of abortion according to gestational time will be depicted using Kaplan-Meier curves.

The primary analysis will be the comparison of the risk of spontaneous abortion during the first 23 weeks of gestation and during the first 19 weeks of gestation in the exposed cohort and the non-exposed cohort using a Cox regression model with spontaneous abortion as the dependent variable, a dichotomous exposure as the independent variable and with age at first day of gestation as a covariate. The HR and its 95% confidence interval (CI) will be derived. The analysis will be done for two risk periods for the exposed subjects: the 30 days before to 45 days after any dose of *Cervarix* period and the 30 days before to 90 days after any dose of *Cervarix* period. The main analysis (primary objective) is the -30 to +45 day risk period.

For subjects with no spontaneous abortion, time-to-event will be censored at: the end of week 23 (or week 19), date of induced or therapeutic abortion, date of death, date of last available pregnancy data whichever occurs first.

The following sensitivity analyses will be performed:

- Cox regression including in addition to the age at the first day of gestation other covariates (region, smoking, alcohol consumption, vaccination, diabetes, high blood pressure, number of previous pregnancies, other vaccination, use of contra-indicated drugs, exposure to H1N1 pandemic)
- Analysis of all abortions (defined as induced, therapeutic and other abortion) using the same model as for the primary analysis

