5.5.3.2. Other endpoints

All other endpoints are binary variables: stillbirths, live births, full term delivery, pre-term and post-term delivery, small for gestational age, large for gestational age, birth defects and baby's death.

The proportion of each outcome will be computed for the exposed and non-exposed cohorts as the number of cases divided by the total number of subjects with known pregnancy outcome. An exact 95% CI will be computed.

The exposed and non-exposed cohorts will be compared using logistic regression with the pregnancy outcome as the dependent variable, a dichotomous exposure as the independent variable and the age at first day of gestation as a covariate. The odds ratio (OR) and its 95% CI will be derived.

Baby characteristics will be summarized per cohort using descriptive statistics: n of non-missing observations, mean, standard deviation, minimum and maximum for continuous variables (birth weight and length) and frequency table (n, %) for categorical variables (sex, Apgar score at 1 and 5 min).

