5.6.2. Descriptive statistics

Age at first day of gestation will be summarized by descriptive statistics per cohort (exposed and non-exposed) and overall: n of subjects, mean, standard deviation (SD), median, minimum and maximum and compared between the two cohorts using a student t-test.

Smoking status (smoker vs. non-smoker), alcohol consumption (Yes/No) will be summarized in frequency tables (n, %) per cohort and overall. The two cohorts will be compared using a Fisher's exact test.

Diabetes and high blood pressure will be summarized in frequency tables (n, %) per cohort and overall. The two cohorts will be compared using a Fisher's exact test.

First day of LMP occurring during the H1N1 pandemic (01JUN2009 to 28FEB2010) will be summarized in frequency tables (n, %) per cohort and overall. The two cohorts will be compared using a Fisher's exact test.

Exposure to other vaccines will also be summarized in frequency tables per cohort and period (within 3 months before first day of gestation and during the 1st trimester of gestation).

Number of subjects exposed to contra-indicated drugs during the 1st trimester of gestation will be tabulated per cohort and overall.

All the pregnancy outcomes (see section 5.2.4.2) and birth defects (see section 5.2.4.3) will be summarized by descriptive statistics per cohort. The statistics will be computed:

- Number of cases
- Proportion computed as the number of cases divided by the total number of pregnancies

All the cases of pregnancy outcome including outcomes with apparent birth defects and baby's deaths will be listed with data about exposure status, age at first day of gestation, gestational age at the event date, smoking status, alcohol consumption, diabetes, high blood pressure, exposure to other vaccines, to contra-indicated drugs and H1N1 pandemic.

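### The descriptive proportion of spontaneous abortion in section 5.5.3.1 counts women who de-enrol before day 161 as non-events, so it understates the absolute risk; the primary hazard ratio is not affected by non-informative withdrawal.

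*Combined protocol and SAP*

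**What the plan says.** For each cohort, section 5.5.3.1 gives the proportion of spontaneous abortion as the "number of pregnant women with spontaneous abortion divided by the total number of included pregnant women". Section 4.3 follows included women to the end of pregnancy, de-enrolment or study termination, so a woman can be included and leave before her outcome is known. The sample size assumptions in 5.4 include "Proportion of dropped out subjects before the first 23 weeks of gestation: 20" per cent. The term is not defined and no figure is given by cohort.

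The comparison of cohorts is a separate matter. Sections 5.5.3.1 and 5.6.3.1 make it an age-adjusted Cox model giving a hazard ratio with a 95% confidence interval, with Kaplan-Meier and model-based curves as displays. Sections 5.2.5.3, 5.5.3.1 and 5.6.3.1 censor women without an event at loss, death, induced or therapeutic abortion, or the end of week 23 (or 19).

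For the other outcomes the denominator changes between sections. Section 5.5.3.2 uses cases "divided by the total number of subjects with known pregnancy outcome". Section 5.6.2, which covers all pregnancy outcomes, says "Proportion computed as the number of cases divided by the total number of pregnancies".

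**The concern.** A woman who de-enrols in week 6 carries the same weight in this denominator as one known to be pregnant at week 24, although most of her risk period was not observed. The numerator can only lose events in this way, so the proportion is biased downward whenever there is early loss.

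The primary objective is to assess the risk of spontaneous abortion, and this proportion is the only numerical absolute risk that the plan specifies for that endpoint. The curves are to be drawn, but no value at day 161 or 133 is requested, and no confidence interval is given for the proportion, whereas 5.5.3.2 asks for an exact interval for the other outcomes. Section 3.2 already sets the CPRD GOLD rate beside literature rates from 7.0% to 14.9%, and readers will probably treat the study result in the same way.

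Section 5.5.1 lists screening, eligibility and inclusion but no count of women lost before day 161 in each cohort, so the size of the shortfall might not be visible in the report.

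**Working it through.** **Inputs.** Risk by week 23, p = 11.5% (5.4). Drop-out before week 23, d = 20% (5.4). Cohorts of 243 exposed (379 in the wider window) and 667 non-exposed (3.2). I treat 11.5% as the risk without loss to follow-up; the plan does not say how it was obtained. The timing of drop-out, its split by cohort and its make-up are not in the documents and are varied below.

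**1. The plan's own figures.** Section 5.4 uses a "two-sided log-rank test with type I error rate of 5" per cent and a "relative risk (Hazard ratio, HR) of 2.0 of spontaneous abortion", and states 98% and 99% power for the two windows. A log-rank calculation of the Lakatos type, with exponential events and exponential 20% drop-out, gives 96.3% and 98.8%, within 2 points of both. The hazard ratios detectable with 80% power come out at 1.72 and 1.63, against the stated 1.69 and 1.60. With no drop-out the power is 97.7% and 99.4%. None of this depends on the crude proportion.

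**2. Shortfall in the proportion.** Let g be the share of a leaver's risk already passed when she leaves. The reported proportion is C = p × [(1 − d) + d × g].

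- All leave at day 0 (g = 0): 0.115 × 0.80 = 9.2%, a shortfall of 2.3 points.
- Even spread (g = 0.5): 0.115 × (0.80 + 0.10) = 10.35%, a shortfall of 1.15 points.
- Three quarters of the risk passed (g = 0.75): 0.115 × (0.80 + 0.15) = 10.9%, a shortfall of about 0.6 points.

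**3. What the 20% contains.** If part of it is induced abortion, those women are observed in full and belong in the denominator of a cumulative incidence. With g = 0.5 and a share a of all women leaving by induced abortion, the target is p × [(1 − a) + a × 0.5], while the reported figure stays at 10.35%.

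- a = 0: target 11.5%, shortfall 1.15 points.
- a = 10%: target 0.115 × 0.95 = 10.9%, shortfall about 0.6 points.
- a = 20%: target 0.115 × 0.90 = 10.35%, no shortfall.

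**4. Unequal withdrawal, an assumption.** With equal withdrawal both cohorts are low by the same factor and the ratio is 1. With a true risk of 11.5% in both cohorts and assumed splits:

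| Withdrawal, exposed / non-exposed | Ratio of proportions, g = 0 | Ratio of proportions, g = 0.5 |
|---|---|---|
| 30% / 10% | 8.05% / 10.35% = 0.78 | 9.8% / 10.9% = 0.89 |
| 10% / 30% | 10.35% / 8.05% = 1.29 | 10.9% / 9.8% = 1.12 |
| 15% / 25% | 9.8% / 8.6% = 1.13 | 10.6% / 10.1% = 1.06 |

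**5. Does it reach the hazard ratio?** This used 500 simulated studies per scenario (243 against 667, true hazard ratio 1, exponential events, withdrawal unrelated to outcome, unadjusted Cox model).

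| Withdrawal, exposed / non-exposed | Crude proportion | Kaplan-Meier at day 161 | Hazard ratio |
|---|---|---|---|
| 20% / 20% | 10.3% vs 10.3% | 11.5% vs 11.5% | 0.98 |
| 30% / 10% | 10.0% vs 11.0% | 11.9% vs 11.6% | 1.02 |
| 10% / 30% | 11.0% vs 9.6% | 11.6% vs 11.4% | 1.01 |

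The crude proportions move with withdrawal. The censored estimates stay at 11.5% and 1 within simulation error.

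**6. Would the known-outcome denominator of 5.5.3.2 repair it?** No. Take known to mean an observed event or follow-up to day 161. At g = 0.5 the denominator is 0.1035 + 0.80 × 0.885 = 0.8115, and 0.1035 / 0.8115 = 12.8%, which overstates 11.5%.

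**The case against.** The strongest reply is that nothing inferential rests on this number. It is one descriptive sentence, with no test, interval or ratio planned, and the analysis that answers the study question censors leavers correctly. That stands. The Kaplan-Meier and model-based curves also show a risk that respects censoring, so the information is partly present; what is missing is a stated value with an interval.

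A reader might go further and infer that unequal withdrawal would produce a false vaccine effect in the primary result. The documents do not support this. Step 5 shows the hazard ratio unmoved by withdrawal unrelated to outcome. Only informative withdrawal could bias it, and nothing in the plan points to that. Unequal withdrawal is itself hypothetical: 5.4 gives one overall figure, and the roughly one-year age difference expected in 3.2 is not linked anywhere to de-enrolment. The ratios in step 4 are statistics that the plan does not compute.

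Two further points also stand. The 9.2% bound is not realistic, because 5.2.5.2 requires another pregnancy identifier after the first day of gestation, so included women have some follow-up. And a loss-to-follow-up row may exist in the Appendix B templates, whose contents are not in the public file; only its absence from 5.5.1 can be confirmed.

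Finally, for spontaneous abortion itself 5.5.3.1 and 5.6.2 broadly agree. The conflict in denominators concerns outcomes such as stillbirth and pre-term delivery, and is a separate defect.

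**Conclusion.** The point holds as a minor one. As written, the rule gives an absolute risk that is too low for the primary endpoint: about 10.4% in place of 11.5% if the whole 20% is loss to follow-up spread evenly over the risk, with 9.2% as an outer bound, and a smaller or no shortfall to the extent that the 20% is induced abortion. These sizes rest on the plan's 11.5% and 20% and on assumed timing. No difference between cohorts follows from the documents, and the primary hazard ratio stands under non-informative withdrawal. The conflict between 5.5.3.2 and 5.6.2 needs no assumption: the same outcome has two defined proportions.

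**What to change.** - **Section 5.5.3.1:** report the cumulative incidence of spontaneous abortion per cohort at day 161 and day 133 with 95% confidence intervals. Treat de-enrolment and death as censoring and induced or therapeutic abortion as a competing event. Show the raw counts beside it.
- **Section 5.5.1:** add the number of women lost before day 161, by cohort and reason, and say whether the 20% in 5.4 includes induced abortions.
- **Sections 5.5.3.2 and 5.6.2:** state one denominator rule for the other outcomes and use it in both.

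The cost is a change of wording and one extra table from data already held. The reported absolute risk will be slightly higher than under the present rule. The Cox analysis does not change.

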- At the time of de-enrolment from CPRD *GOLD*, if during the first 23 weeks (or 19 weeks) of gestation
- At the time of death if during the first 23 weeks (or 19 weeks) of pregnancy.

(Amended 14 March 2013)

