5.6.3. Statistical models

5.6.3.1. Cox proportional hazards model

Cox model will be computed using the SAS PHREG procedure. The dependent variable is the time between first day of gestation and the event or at censoring.

For the spontaneous abortion analysis, time to event for subject with no spontaneous abortion will be censored at the earliest of the following time-points:

- 161 days (end of week 23) or 133 days (end of week 19)
- Lost-to-follow up (*de*-enrolment from CPRD *GOLD*) (**Amended 14 March 2013**)
- Mother's death
- Pregnancy termination

The main model (Model 1) will include the exposure status (exposed vs. non-exposed) as a binary independent variable and the age at first day of gestation as a continuous covariate. The adjusted HR will be derived as the exponential of the coefficient associated with the exposure status and its 95% Wald CI.

Survival curve will be depicted for the exposed and non-exposed cohort (using the Option Plots(overlay)=survival in the SAS PHREG procedure).

The following models will also be computed as sensitivity analyses:

Model 2: A Cox model including, in addition to the age at first day of gestation, other covariates

- Smoking during pregnancy (3 classes: yes, no, unknown)
- Exposure to H1N1 pandemic (yes, no)
- Region (class variable)
- Alcohol consumption during pregnancy (3 classes: yes, no, unknown)
- Diabetes during pregnancy (3 classes: yes, no, unknown)

- High blood pressure during pregnancy (3 classes: yes, no, unknown)
- Number of previous pregnancies (sum of the number of previous births and the number of previous abortions)
- Vaccination with another vaccine within 90 days before first day of gestation or within the 90 days after first day of gestation (binary variable)
- Use of contra-indicated drugs during the first trimester of pregnancy (three classes: non contraindicated drug, manufacturer advice “to-use with caution” drugs, manufacturer mentioned advice “to-avoid” drugs)

Covariates occurring in less than 5% of the subjects (percentage will be computed over both exposed and non-exposed cohorts) will not be included in the model.

Model 3: A Cox model will compare the exposed cohort according to the number of *Cervarix* doses (3 classes: 1 dose, 2 doses, 3 doses) vs. the non-exposed cohort, using the same model as for the primary analysis (model 1). In this model, the exposed women with more than 3 doses of *Cervarix* will not be included.

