Model 4: A Cox model identical to Model 1 will be performed for any abortion occurring before week 24 of gestation. Any abortion will include spontaneous abortion, therapeutic/induced abortion and other abortion.

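### Three sections give different censoring rules for the primary Cox model, and two define the all-abortions event differently

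*Combined protocol and SAP*

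**What the plan says.** Three places set the censoring rule for time to spontaneous abortion.

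- **5.5.3.1** stops follow-up at the end of week 23 (or 19), at induced or therapeutic abortion, "date of death, date of last available pregnancy data whichever occurs first". De-enrolment is not listed.
- **5.6.3.1**, which specifies the Cox procedure, lists "161 days (end of week 23) or 133 days (end of week 19"), loss to follow-up (equated with de-enrolment), the mother's death, and pregnancy termination, which it does not define. Last pregnancy data is not listed.
- **5.2.5.3** applies the week-23 (or 19) limit only to women who are still pregnant at that point. It adds induced or therapeutic abortion, death, and de-enrolment "if during the first 23 weeks (or 19 weeks) of gestation". It lists neither last pregnancy data nor an unresolved 'other abortion'.

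Two places define the event for the all-abortions sensitivity analysis. Section 5.5.3.1 plans "Analysis of all abortions (defined as induced, therapeutic and other abortion) using the same model as for the primary analysis". Model 4 in 5.6.3.1 says "Any abortion will include spontaneous abortion, therapeutic/induced abortion and other abortion".

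**The concern.** Two programmers working from the same document could produce different primary HRs, and the choice between rules could be made after the data are seen. The women affected remain registered while their pregnancy record stops. The inclusion criteria in 4.2.2.1 and 4.2.2.2 do not require a recorded outcome, and 5.5.3.2 restricts its denominators to known outcomes, so the plan seems to expect some unknowns. If these women count as event-free to day 161, miscarriages after their last record are lost while their person-time is kept. That lowers the absolute risk, and it distorts the HR if ascertainment differs between cohorts.

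For the sensitivity analysis, the 5.5.3.1 wording removes the outcome of interest from an analysis meant to cover every abortion.

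**Working it through.** **Where each woman goes under each list**

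| Woman | 5.2.5.3 | 5.5.3.1 | 5.6.3.1 |
|---|---|---|---|
| Registered, no outcome recorded | no rule, unless presumed still pregnant | last pregnancy data | event-free to day 161 (133) |
| De-enrolled before week 23 | de-enrolment | not named; last pregnancy data applies | de-enrolment |
| Unresolved 'other abortion' | not named | not named; last-data rule would ordinarily catch it | pregnancy termination, if that term covers it |

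**The plan's own figures.** Section 5.4 states 98% and 99% power for HR 2.0 ("Using a two-sided log-rank test with type I error rate of 5"%). Inputs: 243 or 379 exposed and 667 non-exposed (3.2); risk 11.5% (5.4). Freedman's formula without loss, 243 v 667:

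- Events = 243 × (1 − 0.885²) + 667 × 0.115 = 52.7 + 76.7 = 129.4.
- φ = 243/667 = 0.364; z = √(129.4 × 0.364) × (2 − 1)/(1 + 0.364 × 2) − 1.96 = 2.01, giving 97.8%.
- The same formula gives 99.4% for 379 v 667.

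The stated power is not in dispute. These inputs serve as the base case.

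**Effect of carrying unknowns to day 161.** Let u₁ and u₀ be the proportions with unknown outcome among exposed and non-exposed, and r the share of their miscarriages recorded before the record stops. None of these is in the documents; all are assumed. Loss is assumed unrelated to outcome. Then, approximately:

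- recorded risk = 11.5% × [1 − u(1 − r)]
- observed HR = true HR × [1 − u₁(1 − r)] / [1 − u₀(1 − r)]

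Suppose 80% of miscarriages fall evenly over weeks 4-12 and last records fall evenly over weeks 5-12 (mean 8.5). Then r = 0.8 × (8.5 − 4)/8 = 0.45.

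- **20% in both cohorts:** 11.5% × (1 − 0.2 × 0.55) = 10.2%, and the HR is unchanged. Simulated cohorts gave 10.2-10.3%, with HR 2.0 reading 1.99-2.00.
- **30% exposed v 10% non-exposed:** ratio (1 − 0.165)/(1 − 0.055) = 0.835/0.945 = 0.88, so 1.0 and 2.0 read 0.88 and 1.77. Simulated Cox fits: 0.88-0.90 and 1.76-1.77.
- **10% v 30%:** ratio 0.945/0.835 = 1.13, so 1.13 and 2.26. Simulated: 1.11-1.14 and 2.24-2.26.
- **Same splits, censored at last record:** close to 1.0 and 2.0, because loss was set to be non-informative.

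The result depends on r. In the extreme r = 0 (no event ever recorded for these women), using the ratio of −ln(1 − recorded risk), 20% in both gives 9.2%, with HR 2.0 reading 1.97. The 30% v 10% split gives 0.77 and 1.51; the reverse gives 1.30 and 2.59.

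For scale, at HR 1.0 the expected events are 243 × 0.115 = 28 and 667 × 0.115 = 77, so SE(log HR) is about √(1/28 + 1/77) = 0.22. A shift from 1.0 to 0.90 (log −0.105) is about half a standard error.

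**All-abortions event.** The 5.5.3.1 bracket leaves out about 910 × 0.115 = 105 expected spontaneous abortions at the base rate. Take spontaneous HR 2.0, no effect on induced abortion, and an assumed 20-40% induced. The cumulative hazards are −ln(0.885) = 0.122 for spontaneous and 0.223 to 0.511 for induced. Model 4 would then show (2 × 0.122 + 0.223)/(0.122 + 0.223) = 1.35, falling to 1.19 at 40%. The 5.5.3.1 event would show 1.00.

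**The case against.** The strongest reply is that this is a wording mismatch whose effect cannot be sized. Much of that stands.

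- A reader might infer that 5.2.5.3 also carries unknowns to day 161. It does not: its week-23 limit is confined to women still pregnant, so it leaves them uncovered.
- A reader might infer that a woman with an unresolved 'other abortion' stays at risk after her pregnancy ended. The 5.5.3.1 last-data rule and the termination item in 5.6.3.1 would ordinarily remove her, and 4.3 ends follow-up at end of pregnancy. Section 5.2.4.2 reclassifies such cases where possible and 5.2.6 sends them to experts, so few should remain. What is left is that 5.2.5.3 does not name the event and 5.6.3.1 does not define its term.
- A reader might take the 20% in 5.4 as the unknown-outcome rate. It is dropout, and de-enrolled women are already censored in 5.2.5.3 and 5.6.3.1.
- Section 5.2.5.2 looks for a further pregnancy identifier before the end of pregnancy, which suggests that an end date usually exists. The algorithms in Appendix A, not in the text reviewed here, may define that date. The denominator in 5.5.3.2 points the other way, so this does not settle the matter.
- Last-record censoring is no cure if records stop because of an unrecorded miscarriage.

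None of this removes the conflict. The lists differ in current text, and no section ranks them.

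**Conclusion.** Wrong as written, and should be fixed; it does not by itself block the study. The primary Cox model has three non-matching censoring lists, and 5.6.3.1 followed literally counts a registered woman with no recorded outcome as event-free to day 161.

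The tempting stronger conclusion, that the primary HR is biased towards no harm, is not supported. With equal unknowns the HR hardly moves; with more unknowns among the non-exposed it rises. Every HR shown rests on assumed unknown rates, assumed timing and non-informative loss. Understatement of absolute risk under the 5.6.3.1 rule follows whenever such women have unrecorded miscarriages, whatever the split.

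The all-abortions conflict is certain on the wording but touches only a sensitivity analysis. Nor would the 5.5.3.1 event be uninformative about misclassification: exposure-related shifting of spontaneous into induced abortion would move its HR. It would simply not be an all-abortions analysis.

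**What to change.** Put one censoring list in 5.2.5.3, 5.5.3.1 and 5.6.3.1: the earliest of

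- day 161 (133) for women known to be still pregnant;
- end of pregnancy by any route that is not the event of that model, including an unresolved 'other abortion';
- de-enrolment;
- death;
- where no outcome is recorded, the last pregnancy record.

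Add the number of women with unknown outcome, by cohort, to the disposition summary in 5.5.1, which does not now list it. Rerun Model 1 with unknowns carried event-free to day 161 as a sensitivity analysis, because last-record censoring assumes non-informative loss. Replace the bracket in 5.5.3.1 with the Model 4 definition: spontaneous, induced/therapeutic and other.

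The cost is wording, slightly less person-time and one extra model run. No change in sample size is needed. The last-record date should be derivable from the extract, but this should be checked against the Appendix A algorithms.
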